2. STUDY PROCEDURES

a. Procedures

Study Design: We will conduct a prospective open label randomized trial comparing effectiveness of duloxetine and desipramine.

Randomization (research): After obtaining research informed consent, the participants are going to be randomized by the treating pain provider using point of care randomization during the clinic visit. Point of care randomization will be done through Collaborative

Health Outcomes Information Registry (CHOIR) using computer generated random numbers.

Intervention: (standard of care) The participants are going to receive either duloxetine or desipramine. Duloxetine will be started at 20 mg per day. It will be increased to 40 mg per day at the beginning of week two, and then to 60 mg per day at the beginning of week three. Desipramine will be started at 25 mg per day. It will be increased to 50 mg per day at the beginning of week two, and then to 75 mg per day at the beginning of week three. These treatments will be continued for at least 6 months provided that the patients can tolerate the side effects and are willing to continue the treatment. Further titration of doses based on participants' tolerance and response is allowed based on clinical decision of the treating pain provider. Concomitant use of other analgesics or pain medications as well as pain interventions are also allowed.

Data collection: (standard of care and research) The participants are going to receive monthly electronic surveys which are already part of their routine clinical care. These surveys are going to be abbreviated to include average and worst Numerical Rating Scale (NRS) of pain; National Institute of Health (NIH) Patient Reported Outcomes Measurement Information System (PROMIS) measures for function, depression and pain interference; and questions about medication compliance, dose and adverse events. Data about use of other analgesics and medications, and pain interventions will also be recorded at these intervals from participants' electronic health records. If the participants do not complete the surveys within five days of receipt of the survey link, they will be contacted to be reminded of the survey. We will also record participants' baseline characteristics including age, sex, main pain diagnosis, other pain diagnoses, psychological comorbidities, medical comorbidities, medication use, and education.

b. Procedure Risks

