Cost of the study medication will be borne by the participants and/or insurance company as part of standard of care. The study itself does not incur any cost in addition to standard of care.

m. **Planned Duration of the Study**

We estimate the study to be completed in 5 years as below:

1. Enrollment: 48 months
2. Follow up for last enrolled patient: 6 months
3. Data analysis and reporting the results: 6 months

7. **RISKS**

a. **Potential Risks**

i. **Investigational devices**

None

ii. **Investigational drugs**

None

iii. **Commercially available drugs, biologics, reagents or chemicals**

Potential adverse events are based on package insert approved by United States Food and Drug Administration:

Duloxetine

Reactions are categorized by body system according to the following definitions: frequent adverse reactions are those occurring in at least 1/100 patients; infrequent

adverse reactions are those occurring in 1/100 to 1/1000 patients; rare reactions are those occurring in fewer than 1/1000 patients.

Cardiac Disorders — Frequent: palpitations; Infrequent: myocardial infarction and tachycardia.

Ear and Labyrinth Disorders — Frequent: vertigo; Infrequent: ear pain and tinnitus.

Endocrine Disorders — Infrequent: hypothyroidism.

Eye Disorders — Frequent: vision blurred; Infrequent: diplopia and visual disturbance.

Gastrointestinal Disorders — Frequent: flatulence; Infrequent: eructation, gastritis, halitosis, and stomatitis; Rare: gastric ulcer, hematochezia, and melena.

General Disorders and Administration Site Conditions — Frequent: chills/rigors; Infrequent: feeling abnormal, feeling hot and/or cold, malaise, and thirst; Rare: gait disturbance.

Infections and Infestations — Infrequent: gastroenteritis and laryngitis.

Investigations — Frequent: weight increased; Infrequent: blood cholesterol increased.

Metabolism and Nutrition Disorders — Infrequent: dehydration and hyperlipidemia; Rare: dyslipidemia.

Musculoskeletal and Connective Tissue Disorders — Frequent: musculoskeletal pain; Infrequent: muscle tightness and muscle twitching.

Nervous System Disorders — Frequent: dysgeusia, lethargy, and paresthesia/hypoesthesia; Infrequent: disturbance in attention, dyskinesia, myoclonus, and poor quality sleep; Rare: dysarthria.

Psychiatric Disorders — Frequent: abnormal dreams and sleep disorder; Infrequent: apathy, bruxism, disorientation/confusional state, irritability, mood swings, and suicide attempt; Rare: completed suicide.

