The study will terminate at the completion of follow-up for last patient enrolled. Study medication will be stopped if the participant decides to discontinue the medication. Since the medications used are part of standard clinical care that the patients receive in our clinic, the participants can continue the medication after the completion of the study if they would like to.

e. Data Safety Monitoring Plan (DSMC)

i. Data and/or events subject to review

The treatments in the study are not different from routine clinical practice; therefore, adverse events will be monitored as a part of participants' clinical care by their clinic providers. Protocol Director (PD) will monitor for protocol deviations.

ii. Person(s) responsible for Data and Safety Monitoring

Data and safety will be monitored by investigators and PD.

iii. Frequency of DSMB meetings

N/A

iv. Specific triggers or stopping rules

N/A

v. Will the Protocol Director be the only monitoring entity? (Y/N)

Yes

f. Risks to Special Populations

N/A

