Comparing Effectiveness of Duloxetine and Desipramine in Patients With Chronic Pain: A Pragmatic Trial Using Point of Care Randomization

Statistical Analysis Plan

NCT03548454

Revised March 28, 2025

Statistical Analysis. The initial sample size calculation determined that 107 participants per group would provide 90% power to detect a one-unit between-group difference in the NRS pain score ($SD=2.25$) at $\alpha=0.05$. However, the study was prematurely stopped due to most referred patients having prior experience with duloxetine or, less frequently, desipramine. As a result, we enrolled 38 patients in the desipramine group and 48 in the duloxetine group. With this sample size, we could detect a difference of 1.37–1.58 in NRS pain reduction with 80–90% power.

Participants were eligible if they completed at least one survey before being assigned a study medication and at least one follow-up survey. The baseline assessment was defined as the most recent survey before treatment assignment. Participants without follow-up surveys or those lost to follow-up were excluded. The primary analysis followed modified intention-to-treat (ITT) principles. However, within the first day of treatment assignment, five individuals switched from desipramine to duloxetine. To account for these switches, a per-protocol (PP) analysis was conducted, categorizing individuals based on the medication they took. For consistency, survey data (research and clinical surveys) were evaluated up to 52 weeks post-baseline when available.

Baseline demographic and clinical characteristics were summarized using three comparative analyses. First, a “per-protocol” approach was applied to compare demographic and clinical characteristics between the desipramine and duloxetine groups. Second, differences were assessed between participants who completed the full course of medication and those who discontinued early. Third, participants who achieved a clinically meaningful ($\geq 30\%$) pain reduction were compared to those who did not. Categorical variables were analyzed using Pearson’s Chi-square or Fisher’s Exact tests, while continuous variables were assessed using t-tests or Mann-Whitney U tests depending on normality.

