Longitudinal changes in pain intensity, physical function, and psychological function were analyzed using linear mixed-effects models (LMMs). Dependent variables included pain intensity (average and worst), PROMIS Pain Interference, PROMIS Anxiety, PROMIS Depression, and PROMIS Physical Function (Upper Extremity, Mobility, and Composite) scores. The primary independent variables were medication group (desipramine vs. duloxetine) and its interaction with time (weeks since baseline) to assess differential treatment effects. Baseline pain intensity was included as a covariate. A random intercept for each participant accounted for within-subject correlations. Various model structures were evaluated using Akaike Information Criterion and Bayesian Information Criterion, with final models selected based on model fit and diagnostic assessments. Model fit was evaluated using residual plots, Q-Q plots, histograms, and Variance Inflation Factor analyses. Bonferroni correction was applied to account for multiple comparisons. LOESS (Locally Estimated Scatterplot Smoothing) predicted values with 95% confidence intervals were plotted to visualize longitudinal trends stratified by medication group.

Kaplan-Meier survival analysis was used to evaluate medication adherence over time, conducted separately for both the intention-to-treat and per-protocol analyses. Time to discontinuation was calculated as the number of days between treatment initiation and discontinuation. Participants who completed the full course of medication were censored at the maximum observed follow-up duration. Kaplan-Meier survival curves were generated for each medication group, and the log-rank test was used to compare groups with 95% confidence intervals. A Kaplan-Meier survival analysis was also conducted to compare the time to achieving a $\geq 30\%$ reduction in average pain intensity from baseline between medication groups. A binary indicator variable was created to determine whether a participant met the pain reduction threshold at any follow-up point, with time-to-event defined as the earliest occurrence of this reduction. Participants who did not achieve the threshold were censored at 52 weeks. Kaplan-Meier survival curves were plotted separately for desipramine and duloxetine, with the log-rank test used for group comparisons.

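### The adherence Kaplan-Meier censors completers at a follow-up time not tied to confirmed drug use, and the full course is undefined, so the curve after month 6 may be too high

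*SAP*

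**What the plan says.** The SAP's adherence analysis puts events on a drug-taking clock: "Time to discontinuation was calculated as the number of days between treatment initiation and discontinuation". Patients who finish treatment are handled differently: "Participants who completed the full course of medication were censored at the maximum observed follow-up duration". The groups are then compared: "the log-rank test was used to compare groups with 95% confidence intervals". The analysis is done for both the intention-to-treat and the per-protocol grouping.

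The SAP gives no length for the full course. Protocol section 2.a gives only a minimum: "These treatments will be continued for at least 6 months provided that the patients can tolerate the side effects". Section 7.d leaves later use open: "the participants can continue the medication after the completion of the study if they would like to". Planned follow-up in section 6.m reads "Follow up for last enrolled patient: 6 months", while the SAP's data window is longer: "survey data (research and clinical surveys) were evaluated up to 52 weeks post-baseline when available". Drug use can be checked in principle, because section 2.a puts "questions about medication compliance, dose and adverse events" in the monthly surveys.

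**The concern.** An adherence curve should keep a patient at risk only while the patient is known to be on the drug. Here the event time is a drug-taking time, but the completers' censoring time is a follow-up time. A patient who takes the drug for six months, stops, and goes on answering clinic surveys to week 52 could be labelled a completer and counted as adherent for the whole year. If the maximum is the cohort's, a completer could also be credited with time in which nobody observed that patient.

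A stop at month 8 has no stated rule. It has a discontinuation date, which suggests an event, but it also exceeds the protocol's minimum, which suggests completion.

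Comparing compliance is a stated aim (protocol section 1.a). The same undefined label also drives the SAP's baseline comparison of completers with early discontinuers and its chi-square test of adherence against pain response.

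**Working it through.** The documents give no adherence rate or stop date, so there is no figure of the plan's own to reproduce on this point. The check is of the rule, with assumed rates.

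**Inputs from the documents.** Course: at least 6 months (protocol 2.a). Survey window: up to 52 weeks when available (SAP). Enrolled: 38 desipramine, 48 duloxetine (SAP).

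**Assumed.** Full course = 182 days (26 × 7); follow-up to day 364 (52 × 7); persistence and later stopping rates as shown.

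**Step 1: the tail.** Let S6 be the proportion on drug at month 6 and q the share of completers who stop between months 6 and 12. If completers cannot have events, the curve at month 12 still reads S6. With late stops as events it reads S6 × (1 − q). The excess is S6 × q. With a constant monthly stopping rate a, q = 1 − (1 − a)^6. Taking S6 = 0.50:

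| a per month | 0.50 × (1 − a)^6 | Curve under the rule | Excess (points) |
|---|---|---|---|
| 0% | 0.500 | 0.50 | 0 |
| 2% | 0.443 | 0.50 | 5.7 |
| 4% | 0.391 | 0.50 | 10.9 |
| 6% | 0.345 | 0.50 | 15.5 |

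**Step 2: simulation with 38 and 48 patients** (300 runs per scenario; early stopping hazard multiplied by 1.3 in one group and 0.8 in the other; late stops spread evenly over days 182 to 364 at the same rate in both groups). Mean month-12 persistence under the rule, against late stops as events:

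- S6 about 50%, no late stops: 0.50 against 0.50
- S6 about 50%, 20% stop late: 0.50 against 0.40
- S6 about 60%, 40% stop late: 0.60 against 0.36
- S6 about 70%, 60% stop late: 0.69 against 0.27

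Over these scenarios the excess runs from 0 to about 42 points (0.69 − 0.27), in line with S6 × q.

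**Step 3: moving the censoring time alone.** Censoring completers at day 364, at day 182 or at the last day on drug gave the same mean month-6 persistence, and the log-rank statistic did not differ in any run (largest difference 0.0). The reason is simple: all events fall on or before day 182, and the risk sets at those times are the same. Censoring at the last day on drug also left the month-12 value where it was (0.50 in the second scenario). It only reduces the number at risk.

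**Step 4: mixed handling.** Suppose 50 of 100 patients are on drug at month 6. Forty have no later follow-up; ten are followed, and four of those stop at month 9 and count as events. If all completers are held to the cohort maximum, persistence after month 9 is 0.50 × 46/50 = 46%. If each is censored at the end of own follow-up, it is 0.50 × 6/10 = 30%. The risk set at an event time now depends on the rule, so the log-rank statistic can too.

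**The case against.** The strongest defence is that the rule may be ordinary Kaplan-Meier practice. The six months is a minimum, the event definition has no upper limit, and a patient who stops at month 8 has a discontinuation date and so may be an event. A completer would then be someone with no stop during observation, and censoring at the end of that patient's own follow-up would be standard. Section 7.d allows continued use, so time after month 6 may be real time on drug. The SAP names 52 weeks for survey data and for the pain-response curve, but not for the adherence curve. If adherence follow-up ended near month 6, there is no tail to overstate.

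All of this is possible, and it makes the bias conditional. It does not remove the point. The SAP does not say that a completer is a patient with no recorded stop, does not require evidence of drug use at the censoring time, and does not say whose maximum applies. The six-month follow-up in section 6.m is stated for the last patient enrolled, and the survey window is longer.

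A reader might go further and infer three things that the documents do not support:

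- *That persistence is overstated as a matter of fact.* No stop dates are given, and the excess is zero if no completer stopped later.
- *That the comparison between drugs is biased.* If no late stop is an event, the log-rank test is unchanged (step 3). Nothing shows that mixed labelling took place.
- *That censoring at the last day on drug would cure it.* By itself it leaves the curve's height unchanged.

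**Conclusion.** The point holds as a conditional weakness in a stated rule, and it is minor. If completion means six months and follow-up runs towards week 52, the adherence curve after month 6 cannot fall and hides any later stop. The excess at month 12 is month-6 persistence times the share of completers who later stop: zero if none do, and 6 to 16 points for 50% persistence with 2% to 6% stopping per month. Those rates are assumed.

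The curve to month 6 stands. The log-rank test is affected only if some late stops are events while other completers stay in the risk set beyond their own confirmed time on drug. The pain models do not use this rule.

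**What to change.** State in the SAP what the full course is for analysis and whose maximum follow-up is meant, and then choose one of two versions.

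1. **End at day 182 (simplest).** Define completion as still taking the drug at day 182, count earlier permanent stops as events, end the curve and the log-rank test at day 182, and print numbers at risk.
2. **Run to week 52.** Count every stop as an event, whenever it occurs, and censor each patient at the last survey that confirms drug use.

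Day 182 is a cut-off for analysis, not a rule for treatment. Use the same completer definition in the completer/discontinuer baseline comparison and in the chi-square test of adherence against pain response.

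The cost is a few lines of SAP text and a rerun of short analyses, using compliance answers already planned in the monthly surveys. Version 1 gives up any adherence claim beyond six months and sets aside later stops that were observed. Version 2 gives a lower and less precise tail where late stops occurred, and its log-rank test answers a different question. In the simulation (50% at month 6, 20% late stops) the mean log-rank chi-square fell from 3.53 to 3.08, because late stopping was set equal in the two groups.

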To assess the relationship between medication adherence and the likelihood of achieving meaningful pain reduction, a chi-square test was conducted. The proportion of participants who achieved a $\geq 30\%$ pain reduction was compared between those who completed the full course of medication and those who discontinued early

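### Non-responders are censored at 52 weeks even if their surveys ended earlier, so the time-to-≥30%-reduction curve counts unobserved weeks as observed non-response

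*SAP*

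**What the plan says.** All SAP text on this point is in its single section, Statistical Analysis.

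- **Event.** A binary indicator records "whether a participant met the pain reduction threshold at any follow-up point", and the event time is the first such occasion.
- **Censoring.** "Participants who did not achieve the threshold were censored at 52 weeks". No alternative is given for participants whose surveys ended sooner.
- **Who is analysed.** "Participants were eligible if they completed at least one survey before being assigned a study medication and at least one follow-up survey". Also: "Participants without follow-up surveys or those lost to follow-up were excluded". Loss to follow-up is not defined.
- **Data window.** "survey data (research and clinical surveys) were evaluated up to 52 weeks post-baseline when available".
- **Related test.** In the closing chi-square, the proportion with a ≥30% "pain reduction was compared between those who completed the full course of medication and those who discontinued early".

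The Protocol, section 2.a (Data collection), says: "The participants are going to receive monthly electronic surveys which are already part of their routine clinical care". Section 6.m (Planned Duration of the Study) lists "Follow up for last enrolled patient: 6 months".

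**The concern.** A response can be recorded only at a completed survey. Once surveys stop, nobody knows whether the participant would have crossed the threshold. Kaplan-Meier handles this by removing the participant from the risk set at the last observation. The SAP instead keeps every non-responder at risk to week 52, so someone with a single survey at month 1 counts as event-free for a full year.

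Two results are at stake. The cumulative response curves read low if dropout is unrelated to response. The log-rank comparison of the arms is distorted if survey follow-up differs between them, because the arm that stops answering sooner appears to respond less.

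Treating missing follow-up as non-response can be a legitimate estimand, but the SAP does not name it, and a reader would take the curves for ordinary censored estimates.

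A secondary point concerns the chi-square of response by medication completion. It appears to use the same indicator of response at any survey. If completers answered more surveys, they had more chances to be counted as responders. The documents give no survey counts, so this remains conditional.

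**Working it through.** The SAP states no response rate, survey-completion rate or number at risk for this analysis, so there is no figure of its own to reproduce. Its sample-size figures concern mean NRS scores and do not bear on this point.

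**Step 1: what the rule does, without assumptions.** The Kaplan-Meier survival estimate is the product over event times of (n_j − d_j)/n_j, where n_j is the number at risk and d_j the number of events. If nobody is censored before week 52, then n_(j+1) = n_j − d_j and the product telescopes to (n − all responders)/n. The week-52 response estimate is therefore documented responders divided by all analysed, whatever the follow-up.

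**Step 2: half the surveys end at month 6.** Assume a constant response rate, true 12-month response p, and dropout unrelated to response. The SAP curve then reads 0.5 × [1 − √(1 − p)] + 0.5 × p.

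- p = 0.60: 0.5 × 0.368 + 0.5 × 0.60 = 0.484
- p = 0.40: 0.5 × 0.225 + 0.5 × 0.40 = 0.313

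**Step 3: gradual dropout.** Inputs from the documents are 38 and 48 participants (SAP), monthly surveys (Protocol 2.a) and at least one follow-up survey (SAP). Assumptions are 12 surveys to week 52, the same true response in both arms, and monthly dropout d unrelated to response. With s = (1 − p)^(1/12), q = 1 − s and r = s(1 − d), the expected SAP curve at month 12 is q(1 − r^12)/(1 − r). The share still surveyed at month 12 is (1 − d)^11.

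Example, p = 0.60 and d = 0.10: s = 0.9265, q = 0.0735, r = 0.8338, r^12 = 0.113. The curve reads 0.0735 × 0.887/0.1662 = 0.39, and 0.90^11 = 31% are still surveyed.

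Log-rank false-positive rates at the 0.05 level come from simulation (5,000 runs per row):

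| Monthly dropout, 38-arm vs 48-arm | Still surveyed at month 12 | SAP curves, true 60% | False positives | SAP curves, true 40% | False positives |
|---|---|---|---|---|---|
| 10% vs 10% | 31/31% | 39/39% | 5% | 25/25% | 5% |
| 10% vs 7% | 31/45% | 39/44% | 6% | 25/29% | 6% |
| 10% vs 5% | 31/57% | 39/48% | 12% | 25/31% | 9% |
| 15% vs 5% | 17/57% | 33/48% | 24% | 21/31% | 18% |
| 20% vs 5% | 9/57% | 28/48% | 42% | 17/31% | 31% |

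Repeat simulations with separate code agree to within about three percentage points. At true 60%, censoring at the last survey gives 59–60% and about 5% false positives in every row. A separate set of assumptions (surveys every 4 weeks, true response 50%) gives SAP-rule false positives of 16% for dropout of 15% vs 7% per survey, and 39% for 25% vs 7%.

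**Step 4: the opposite case.** Suppose only participants who would not respond by month 12 drop out, with true response 60%. The SAP rule is then right: 60/60% and 5% false positives. Last-survey censoring overstates response:

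| Monthly dropout | Last-survey curves | False positives |
|---|---|---|
| 10% vs 10% | 77/77% | 5% |
| 10% vs 5% | 77/68% | 9% |
| 15% vs 5% | 85/68% | 17% |
| 20% vs 5% | 91/68% | 29% |

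Neither rule is safe alone.

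**The case against.** The strongest reply is that participants lost to follow-up were excluded, and that this is listed separately from having no follow-up survey, so it should remove some people with partial data. If it removed everyone without surveys to week 52, the rule would do no harm. But the term is undefined, the stated minimum is one follow-up survey, and data to 52 weeks are used only where available. Nothing requires complete follow-up.

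The sentence may also be shorthand for an administrative maximum. That is possible, but the text does not say so. If the code in fact censored at the last survey, one sentence settles the matter.

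Several limits stand:

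- The 6-month entry in the Protocol is a planned timeline for the last patient. Clinical surveys may continue beyond it, so it is only supporting evidence.
- The high error rates need a three- to fourfold difference between arms in monthly dropout, and the documents show no such gap.
- Analysed numbers may be below 38 and 48. With an assumed 30 vs 40, false positives in the last two rows at true 60% fall from 24% and 42% to about 20% and 35%.
- Last-survey censoring is itself biased when non-responders selectively stop answering (Step 4). This is why both analyses should be reported.

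**Conclusion.** The concern holds: the censoring rule is wrong as written. That the week-52 estimate reduces to documented responders over all analysed follows from the text alone, provided some non-responders' surveys ended early, which the inclusion rule and data window allow.

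The size is conditional. With dropout unrelated to response, the assumed scenarios put the SAP curves at 28–48% against a true 60%, and false positives between 5% (equal follow-up) and 42% (very unequal follow-up). With dropout confined to non-responders, the SAP rule is unbiased. Without last-survey times by arm, neither size nor direction in this trial can be determined.

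This is a supplementary analysis and the mixed models do not depend on it. It is nevertheless a between-arm test on the threshold that the SAP itself calls clinically meaningful, so it should be fixed. The chi-square point is secondary.

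**What to change.** 1. Censor each participant without a ≥30% reduction at his or her own last completed average-pain survey, at most week 52, and state that this assumes dropout unrelated to response.
2. Keep the 52-week rule as a sensitivity analysis, labelled non-responder imputation, and report both results.
3. Show numbers at risk under the curves and the distribution of last-survey time by arm.
4. Define loss to follow-up and say how many participants it excluded from each arm.
5. For the completion-by-response chi-square, compare the groups over equal observation, for example response at a fixed survey by medication status at a landmark time.

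The cost is a few sentences in the SAP and a re-run of existing code on data already held. Late Kaplan-Meier intervals will be wider. If non-responders selectively stopped answering, the new main curve will overstate response, and the sensitivity analysis lets a reader judge that.
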